**Figure 2 Hierarchical testing of hypothesis**

\* Alpha split equally between rMenB+OMV NZ and MenABCWY vaccine objectives.

If all rMenB+OMV NZ objectives are achieved, MenABCWY vaccine objectives will be tested at full alpha.

**CONFIDENTIAL**205416 [MENB REC 2ND GEN-038 (V72\_72)]  
Protocol Amendment 4 Final

\*\* If all objectives of rMenB+OMV NZ are met, the comparator will be the 0,2-months schedule. If the 0,2-months objective is not met, and the 0,6-months is met, then the 0,6-months schedule will be the comparator. If the 0,6-months is also not met, then the 0,2,6-months schedule will be the comparator.

Refer to [Glossary of terms](#) for definitions of test-based and responder-based vaccine effectiveness.

An explanation of the hypothesis testing is given in the following subsections:

#### **10.1.1.1. Vaccine effectiveness (Test-based): rMenB+OMV NZ - 3 doses (0,2,6-months schedule)**

For demonstration of VE of rMenB+OMV NZ the following hypothesis will be tested:

***Null hypothesis:***

***H0: VE ≤ 65%***

***vs. Alternative hypothesis:***

***H1: VE > 65%***

Where, VE represents the vaccine effectiveness, defined as  $1 - RR = (1 - \text{percentage of samples without bactericidal serum activity measured by enc-hSBA at a 1:4 dilution in the MenB group} / \text{percentage of samples without bactericidal serum activity at 1:4 dilution in the ACWY group}) \times 100\%$  and 65% is the pre-specified success criteria for VE. The VE against all 110 strains combined and associated 97.5% CI, will be computed by means of a generalised linear model. If the lower limit of the 97.5% CI for VE is > 65% effectiveness will be claimed.

#### **10.1.1.2. Effectiveness (Responder-based): rMenB+OMV NZ - 3 doses (0,2,6-months schedule)**

A responder is defined as a subject with at least 70% of the strains killed in sera, one month after vaccination schedule.

***Null hypothesis:***

***H0:  $\pi_B \leq 65\%$***

***vs.***

***Alternative hypothesis:***

***H1:  $\pi_B > 65\%$***

Where  $\pi_B$  represents the percentages of responders observed at one month after vaccination schedule; and 65% is the pre-specified success criterion for the responder-

**CONFIDENTIAL**205416 [MENB REC 2ND GEN-038 (V72\_72)]  
Protocol Amendment 4 Final

based endpoint. The objective is to demonstrate that the lower limit of the 97.5% CI for the percentage of responders is higher than 65%.

**10.1.1.3. Vaccine effectiveness (Test-based): rMenB+OMV NZ - 2 doses (0,6-months schedule)**

See Section [10.1.1.1](#)

**10.1.1.4. Effectiveness (Responder-based): rMenB+OMV NZ - 2 doses (0,6-months schedule)**

See Section [10.1.1.2](#)

**10.1.1.5. Vaccine effectiveness (Test-based): rMenB+OMV NZ - 2 doses (0,2-months schedule)**

See Section [10.1.1.1](#)

**10.1.1.6. Effectiveness (Responder-based): rMenB+OMV NZ - 2 doses (0,2-months schedule)**

See Section [10.1.1.2](#)

**10.1.1.7. Lot-to-lot consistency: MenABCWY - ACWY component**

For demonstration of lot-to-lot consistency, the following equivalence hypotheses will be tested simultaneously for each of the 4 serogroups A, C, W, Y:

***Null hypothesis:***

$$H_0: (\mu_{lot\ 1(i)} - \mu_{lot\ 2(i)}) \leq \log_{10}(0.5) \text{ or } (\mu_{lot\ 1(i)} - \mu_{lot\ 2(i)}) \geq \log_{10}(2) \text{ or}$$

$$(\mu_{lot\ 1(i)} - \mu_{lot\ 3(i)}) \leq \log_{10}(0.5) \text{ or } (\mu_{lot\ 1(i)} - \mu_{lot\ 3(i)}) \geq \log_{10}(2) \text{ or}$$

$$(\mu_{lot\ 2(i)} - \mu_{lot\ 3(i)}) \leq \log_{10}(0.5) \text{ or } (\mu_{lot\ 2(i)} - \mu_{lot\ 3(i)}) \geq \log_{10}(2)$$

vs.

$$H_1: (\mu_{lot\ 1(i)} - \mu_{lot\ 2(i)}) > \log_{10}(0.5) \text{ and } (\mu_{lot\ 1(i)} - \mu_{lot\ 2(i)}) < \log_{10}(2) \text{ and}$$

$$(\mu_{lot\ 1(i)} - \mu_{lot\ 3(i)}) > \log_{10}(0.5) \text{ and } (\mu_{lot\ 1(i)} - \mu_{lot\ 3(i)}) < \log_{10}(2) \text{ and}$$

$$(\mu_{lot\ 2(i)} - \mu_{lot\ 3(i)}) > \log_{10}(0.5) \text{ and } (\mu_{lot\ 2(i)} - \mu_{lot\ 3(i)}) < \log_{10}(2)$$

Where  $\mu_{lot\ 1(i)}$ ,  $\mu_{lot\ 2(i)}$  and  $\mu_{lot\ 3(i)}$  denote the means of log10-transformed titres for serogroups i=A, C, W and Y at 1 month after the second vaccination of the corresponding lot groups; and 0.5-2.0 are the non-inferiority margins for the ratio of GMTs between each pair of lots. Lot-to-lot consistency will be claimed if the two-sided 97.5% CIs for

**CONFIDENTIAL**205416 [MENB REC 2ND GEN-038 (V72\_72)]  
Protocol Amendment 4 Final

the ratio of hSBA GMTs of antibodies against serogroups A, C, W and Y are within the [0.5;2.0] equivalence interval for each pair of lots.

**10.1.1.8. Immunological non-inferiority: MenABCWY vs. MenACWY**

For demonstration of non-inferiority of MenABCWY vs MenACWY in subjects without a previous MenACWY vaccination (unprimed), the following non-inferiority hypotheses will be tested simultaneously for each of the 4 serogroups A, C, W, and Y:

*Null hypothesis:*

$$H_0: \pi_{ABCWY} - \pi_{ACWY} \leq -10\%$$

vs.

*Alternative hypothesis:*

$$H_1: \pi_{ABCWY} - \pi_{ACWY} > -10\%$$

Where:  $\pi_{ABCWY}$  represents the percentages of subjects with a 4-fold rise 1 month after the last vaccination in the ABCWY group (pooled lots) and  $\pi_{ACWY}$  represents the percentage of subjects with a 4-fold rise 1 month after the first vaccination in the ACWY group; and -10% is the non-inferiority margin for the difference in between ABCWY group (pooled lots) and ACWY group. Immunological non inferiority of MenABCWY to MenACWY will be claimed if the LL of the 2-sided 97.5% CI for the group difference in percentages of subjects achieving a 4-fold rise in hSBA titres is above -10% for each serogroup.

**10.1.1.9. Vaccine effectiveness (Test-based): MenABCWY**

See Section [10.1.1.1](#)

**10.1.1.10. Effectiveness non-inferiority: MenABCWY vs. rMenB+OMV NZ**

For demonstration of non-inferiority of the VE of MenABCWY compared to the VE of rMenB+OMV NZ the following hypothesis will be tested:

*Null hypothesis:*

$$H_0: \pi_{ABCWY} - \pi_{Control} \leq -5\%$$

vs.

*Alternative hypothesis:*

$$H_1: \pi_{ABCWY} - \pi_{Control} > -5\%$$

**CONFIDENTIAL**205416 [MENB REC 2ND GEN-038 (V72\_72)]  
Protocol Amendment 4 Final

Where:  $\pi_{ABCWY}$  and  $\pi_{Control}$  represent the percentages of samples with bactericidal serum activity at 1:4 dilution in the ABCWY group (pooled lots) 1 month after the last MenABCWY vaccination and in the MenB group one month after the last rMenB+OMV NZ vaccination of the final schedule as determined in this study; and -5% is the non-inferiority margin for the difference in percentages of samples with bactericidal serum activity between ABCWY (pooled lots) and MenB group. Non inferiority of MenABCWY to rMenB+OMV NZ will be claimed if the LL of the 2-sided 97.5% CI for the group difference in percentages of samples with bactericidal serum activity at 1:4 dilution is above -5%.

**10.1.1.11. Effectiveness (Responder-based): MenABCWY**

See Section [10.1.1.2](#)

**10.1.2. Sample size justification**

Overall study sample size and its power is provided in Section [10.1](#). This sub-section provides a breakdown of the power calculation for each of the objectives. All calculations are based on number of evaluable subjects.

**10.1.2.1. Vaccine effectiveness (Test-based): rMenB+OMV NZ - 3 doses (0,2,6-months schedule)**

The planned (target) number of strains to be tested for each subject will be 35 strains. A minimum amount of 5 mL of serum needs to be available to perform enc-hSBA testing. In case the volume of serum shipped to the laboratory for enc-hSBA testing is <5 mL, enc-hSBA testing will be still performed if the volume of serum allows to test a minimum number of 20 strains. Otherwise no enc-hSBA testing will be performed with the specific sample. The power was calculated for two situations: 30 and 35 strains to be tested per subject.

In study V102\_16E1, the observed raw percentages of samples without bactericidal serum activity at 1:4 dilution were 77.8% in the MenACWY vaccine group and 21.9% in the MenABCWY group one-month post 3rd vaccination. The estimated VE of MenABCWY compared to MenACWY was 71% (95% CI: 69% - 73%). For the sample size calculations, it is assumed that MenB (any schedule) will have similar results as MenABCWY 0,2,6-months.

[Table 18](#) shows the result of power calculation for a group size of 684 evaluable subjects in MenB group, (any schedule) and 137 subjects in MenACWY group. The percentage of tests without bactericidal serum activity for MenACWY is assumed to be 75%, while the estimation for MenB is 22%. Sample size calculations revealed >99.9% power to show that the lower limit of the two-sided 97.5% CI for the VE is >65% (Refer to Section [10.1.1.1](#))

**CONFIDENTIAL**205416 [MENB REC 2ND GEN-038 (V72\_72)]  
Protocol Amendment 4 Final**Table 18 Power for VE 65% against all 110 strains combined, any schedule**

% of tests without bactericidal serum activity at 1:4 dilution		Power			
MenACWY	MenB	Vaccine Effectiveness	Success Criterion (LL of 97.5% CI)	30 strains per subject	35 strains per subject
75%	20%	73%	>65%	99.9%	99.9%
77%	20%	74%	>65%	99.9%	99.9%
75%	22%	71%	>65%	99.9%	99.9%
77%	22%	71%	>65%	99.9%	99.9%
75%	25%	67%	>65%	84.4%	89.3%
77%	25%	68%	>65%	99.8%	99.9%

LL: lower level, CI: Confidence Interval, VE: Vaccine Effectiveness

\* Computed by 10,000 simulation runs each based on SAS GENMOD procedure.

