**5.3. Number of subjects**

A total of 3651 subjects will be randomised in a ratio of 5:5:3:3:3:1; 912 each in MenB\_0\_2\_6 and MenB\_0\_6 groups, 548 in each ABCWY groups and 183 in ACWY group. Assuming a 25% drop-out rate, this should provide approximately 684 evaluable subjects in the MenB groups, 411 evaluable subjects in the ABCWY groups and 137 evaluable subjects in the ACWY group.

Refer to Section 10.1 for a detailed description of the criteria used in the determination of sample size.

Withdrawals will not be replaced.

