### 10.1.1. Hypothesis testing strategy

Multiple objectives and endpoints require type I error control. Full alpha (0.05) is split equally (alpha=0.025) between rMenB+OMV NZ objectives and MenABCWY objectives. Furthermore, within rMenB+OMV NZ, as well as within MenABCWY, objectives are tested hierarchically. If the first null hypothesis is rejected, then the testing will continue with the second hypothesis at same alpha. Same for 3rd, 4th, and so forth. Whenever a null hypothesis is not rejected, then the testing will stop.

As the comparator for MenABCWY non inferiority objective for the B component will be the selected schedule of rMenB+OMV NZ as determined in this study, the objectives of rMenB+OMV NZ will be analysed first. Additionally, if all null hypotheses related to rMenB+OMV NZ objectives will be rejected, the alpha (alpha=0.025) will be propagated to the MenABCWY part, and hypotheses related to MenABCWY objectives will be tested at full alpha (alpha=0.05). See Figure 2 for an explanation of the hierarchical testing (top to bottom, the order indicated by the arrows).

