**10.3.3.1. Vaccine effectiveness (Test-based): rMenB+OMV NZ - 3 doses (0,2,6-months schedule)**

Analysis set: Per-protocol set (PPS) will be the primary analysis population

Statistical method: The VE is defined as  $1 - RR = (1 - \text{percentage of samples without bactericidal serum activity at 1:4 dilution in MenB group} / \text{percentage of samples without bactericidal serum activity at 1:4 dilution in the Control group}) \times 100\%$  and it will be analyzed using a generalised linear model with vaccine group, strain and centre as independent variables. Furthermore, a repeated statement will be used to estimate the variance of the RR including correlation within subject's responses. A centre effect will be tentatively included in the analysis; if the statistical model does not converge due to

**CONFIDENTIAL**205416 [MENB REC 2ND GEN-038 (V72\_72)]  
Protocol Amendment 4 Final

the factor “centre”, a model without centre effect will be fitted instead. The response variable of the model will be the Bernoulli distributed outcome without bactericidal activity at a 1:4 dilution (i.e. response is 1 if titre < 4, and 0 if titre ≥ 4), at 1 month after the last vaccination (Month 7) in the MenB group and at Month 1 for the ACWY group. Each subject will contribute with approximately 35 measures to this analysis, each of the measures corresponding to the response variable to one of the 35 strains randomly assigned to be tested with the samples available for that specific subject. For the statistical analysis it is assumed that the response to each strain is an independent measure with a unique true underlying rate and VEs are expected to vary among the strains. In order to obtain the VE measure which is a measure based on the relative risk (RR), a generalised linear model will be used with the Binary distribution and link function log in order to compute the log RR and the corresponding 97.5% CI. If this model would not converge, the Poisson distribution will be used instead. The obtained values will be exponentiated to obtain the RR and the corresponding 97.5% CI. The VE will be computed as  $100\% \times (1 - RR)$ . Effectiveness of rMenB+OMV NZ will be demonstrated if the lower limit of the two-sided 97.5% CI for VE against the selected strain panel between MenB and the ACWY group is above 65%.

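### Table 18's power for the 25% MenB rows reproduces only with independent strain results within a subject, whereas the planned analysis includes within-subject correlation; the 75/25 row is therefore optimistic by an uncertain amount

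*Protocol*

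**What the plan says.** Section 10.1.2.1 sets the test-based power for a "group size of 684 evaluable subjects in MenB group, (any schedule) and 137 subjects in MenACWY group". Success requires that the "lower limit of the two-sided 97.5% CI for the VE is >65" percent. On strain counts it says: "The power was calculated for two situations: 30 and 35 strains to be tested per subject". The results are in Table 18, whose footnote reads "Computed by 10,000 simulation runs each based on SAS GENMOD procedure". Neither text nor table says how results within one subject were correlated in the simulated data.

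Section 10.3.3.1 describes the analysis. It says that "a repeated statement will be used to estimate the variance of the RR including correlation within" a subject's responses. Further on it says: "For the statistical analysis it is assumed that the response to each strain is an independent measure with a unique true underlying rate", and adds that effectiveness is expected to differ between strains.

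Sections 10.1.2.3, 10.1.2.5 and 10.1.2.9 give no separate test-based power for the 0,6 and 0,2 schedules of rMenB+OMV NZ or for two-dose MenABCWY. They refer back to Section 10.1.2.1.

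**The concern.** Each subject contributes 30 or 35 yes/no results from one serum sample. A subject with a strong response will tend to kill many strains and a weak responder few, so the results are likely to be positively correlated. The repeated statement widens the interval to allow for this. If the power simulation did not generate such correlation, Table 18 describes a narrower interval than the one to be reported.

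Where true effectiveness is well above 65% this makes no practical difference. It matters close to the criterion. Section 3.1 reports 67% after two doses of MenABCWY in the earlier study, which is the effectiveness in the 75/25 row. Table 18 is applied unchanged to the two-dose primary hypotheses, and under Section 10.1.1 testing stops at the first hypothesis that is not rejected. A reader would take about 89% as the power in that situation.

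**Working it through.** **Inputs.** Evaluable subjects: 684 (MenB) and 137 (ACWY), after the step "Assuming a 25% drop-out rate" in Section 5.3 (912 × 0.75 = 684; 183 × 0.75 ≈ 137). Strains per subject m = 30 or 35. Alpha: "Full alpha (0.05) is split equally (alpha=0.025) between rMenB+OMV NZ objectives and MenABCWY objectives" (Section 10.1.1), so a 97.5% interval and z = 2.2414. Criterion: VE > 65%, that is RR < 0.35.

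**Formula, all strain results independent.**

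Var(log RR) = (1 − pB)/(684 × m × pB) + (1 − pA)/(137 × m × pA)

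Power = Φ( [ln 0.35 − ln(pB/pA)] / SE − 2.2414 )

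**Reproducing Table 18.**

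- 75/25: distance = ln 0.35 − ln(0.25/0.75) = 0.0488. At m = 35, Var = 0.0001253 + 0.0000695 and SE = 0.01396, so power = Φ(3.496 − 2.241) = 89.5%. At m = 30, SE = 0.01508 and power = 84.0%.
- 77/25: distance = 0.0751. At m = 35, SE = 0.01370 and power = 99.9%. At m = 30, SE = 0.01479 and power = 99.8%.

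| Row | Strains | Stated | Independent results |
|---|---|---|---|
| 75/25 | 30 | 84.4% | 84.0% |
| 75/25 | 35 | 89.3% | 89.5% |
| 77/25 | 30 | 99.8% | 99.8% |
| 77/25 | 35 | 99.9% | 99.9% |

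For the 75/25 row, 5,000 simulated trials without correlation, analysed with a subject-level robust variance, gave 83.7% and 89.4%. Other constructions do not fit that row: a 95% interval gives 89.9% and 93.8%, a Poisson model-based variance 46.0% and 52.8%, and one result per subject (m = 1) 4.9%. The 20% and 22% rows are near 100% with or without correlation and are uninformative.

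**Corroboration from Table 22.** With 684 × 35 = 23,940 independent tests per group and a margin of −5%, SE for 75% vs 78% is √[(0.75 × 0.25 + 0.78 × 0.22)/23,940] = 0.00387, and power = Φ(0.02/0.00387 − 2.2414) = 99.8%. For 75% vs 79% it is 64.1%. The table states 99.8% and 64%. With 684 independent units the results would be 8.6% and 3.6%.

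**Adding correlation.** Multiply the variance by a design effect DE = 1 + (m − 1) × ICC. The protocol gives no ICC, so this is an assumed range, at 35 strains:

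| DE | ICC | 75/25 (stated 89.3%) | 77/25 (stated 99.9%) | 75/22 |
|---|---|---|---|---|
| 1.2 | 0.006 | 83% | 99.7% | >99.9% |
| 1.45 | 0.013 | 75% | 99.0% | >99.9% |
| 1.8 | 0.024 | 64% | 96.8% | >99.9% |

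**What the protocol's prior data say about the size.** Two figures from V102_16E1 point in different directions.

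- Responder data: 21.9% of tests were without activity, so 78.1% were killed, and 78.5% of subjects killed at least 70% of strains (Section 10.1.2.2). With 35 independent tests at 78.1%, 87.5% of subjects would reach 25 of 35. That lies above the reported interval of 68.8% to 86.3%. A beta-binomial matches 78.5% at an ICC of about 0.039, DE about 2.3.
- VE interval: 69% to 73% gives SE(log RR) = ln(0.31/0.27)/3.92 = 0.035. The responder interval fits 73 of 93 subjects. With 93 subjects, 30 to 35 strains and any control group of 20 or more, the independence SE is about 0.033 to 0.042, so DE is roughly 0.7 to 1.1. Taking the widest limits that rounding allows (68.5% to 73.5%), SE = 0.044 and DE is at most about 1.7 for control groups of up to 200.

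**The case against.** The strongest reply is that nothing the trial depends on changes. The planning case is 75/22, where power stays above 99.9%; 75/25 is a sensitivity row. The observed control rate in V102_16E1 was 77.8%, nearer to 77% than 75%, and the 77/25 row barely moves. This stands, and it limits the point to a correction of stated figures. A reader might infer that the trial is too small, or that the planned analysis cannot support an effectiveness claim; the documents support neither.

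The second reply is about size. A reader might take the design effect of 2.3 as established and quote about 52% power for the 75/25 row (about 91% for 77/25). That figure rests on a strain count per subject in the prior study that is not stated, on a beta-binomial shape and on one responder percentage; the upper end of that percentage's own interval corresponds to a design effect of only about 1.1 to 1.2. The prior VE interval suggests about 1. That source is not decisive either, because the protocol does not say whether the interval allowed for clustering. The size is therefore open.

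Third, the independence sentence in Section 10.3.3.1 might be read as an invalid analysis that contradicts the repeated statement. It does not have to be. In context it can mean that each strain has its own rate, in a model that includes strain, and the planned variance is clear from the repeated statement. The wording is loose, not wrong in effect.

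Finally, independence in the simulation is inferred from matching numbers. Strain-to-strain variation with strain adjustment can raise power: in a 1,000-run check at 75/25 and 30 strains, a between-strain SD of 0.10 to 0.20 in the control rate gave 84% to 89% with no subject correlation, and 75% to 77% at a latent correlation of 0.02. An exact offset in both informative rows would be a coincidence, but it cannot be excluded from the text.

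**Conclusion.** The point holds as a correction to stated power. The 25% MenB rows of Table 18 match independent strain results and none of the alternatives tried, while the planned variance includes within-subject correlation. The 75/25 row is the one materially affected: about 83% to 64% instead of 89.3% over an assumed design effect of 1.2 to 1.8 at 35 strains. The 77/25 row stays at about 97% or higher. The planning case, the sample size and the decision rule are unaffected.

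The direction rests on within-subject correlation being positive, which the responder data support. The amount rests on a correlation that the protocol does not give and on which its two prior-study figures disagree.

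**What to change.** Re-run the Table 18 simulation with a subject-level correlation over a stated range, analysed with the planned repeated statement. Give the assumed correlation in the footnote and restate the 25% MenB rows. Sections 10.1.2.3, 10.1.2.5 and 10.1.2.9 rely on the same table and need no text of their own beyond the cross-reference.

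As an editorial clarification in Section 10.3.3.1, say that independence between strain results is only the working correlation, that each strain has its own underlying rate, and that inference uses the variance clustered by subject.

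The cost is one simulation re-run and less favourable figures in the 75/25 row. Conduct, sample size and success criteria do not change.

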**10.1.2.2. Effectiveness (Responder-based): rMenB+OMV NZ - 3 doses (0,2,6-months schedule)**

Post-hoc calculations for study V102\_16E1 were performed following a regulatory agency request. The calculated percentage of responders of subjects with  $\geq 70\%$  of tested strains killed was 78.5% (95% CI [68.8%; 86.3%]) in the MenABCWY group one-month post 3rd vaccination. To have overall power of 90% (refer to Section 10.1), the effectiveness (responder-based) endpoint needs to have 97% power. Six hundred eighty-four (684) evaluable subjects will be necessary to demonstrate with at least 97% power that the lower limit of the 97.5% CI for proportion of responders in the MenB group (any schedule) is above 65% assuming the expected percentage in the study is 72.5% (see Table 19 below).

**Table 19 Power for rMenB+OMV NZ Responder-based analysis 3 dose (0,2,6-months schedule)**

N	% Responders – MenB	Success Criterion	Power
684	69%	65%	48.4%
684	72.5%	65%	97.6%
684	75%	65%	>99.9%

**10.1.2.3. Vaccine effectiveness (Test-based): rMenB+OMV NZ - 2 doses (0,6-months schedule)**

As the underlying assumptions for the rMenB+OMV NZ schedules are the same, see Section 10.1.2.1.

**10.1.2.4. Effectiveness (Responder-based): rMenB+OMV NZ - 2 doses (0,6-months schedule)**

As the underlying assumptions for the rMenB+OMV NZ schedules are the same, see Section 10.1.2.2.

**10.1.2.5. Vaccine effectiveness (Test-based): rMenB+OMV NZ - 2 doses (0,2-months schedule)**

As the underlying assumptions for the rMenB+OMV NZ schedules are the same, see Section 10.1.2.1.

**CONFIDENTIAL**205416 [MENB REC 2ND GEN-038 (V72\_72)]  
Protocol Amendment 4 Final**10.1.2.6. Effectiveness (Responder-based): rMenB+OMV NZ - 2 doses (0,2-months schedule)**

As the underlying assumptions for the rMenB+OMV NZ schedules are the same, see Section [10.1.2.2](#).

